The total number of patients that will be randomized in the study has been increased from 100 to approximately 138. The reason for increasing the total number of patients is to make sure that there are enough patients to evaluate the sustained effect on CFVR after 12 weeks, that is, about 33 evaluable patients per arm for AZD5718 [REDACTED] and placebo. An evaluable patient is defined as a patient with a valid CFVR measurement at Visit 2 (baseline), and one postbaseline visit as judged by the CFVR Core lab. The total number of patients for evaluation of uLTE₄ and CFVR at week 4 will be more than 33 patients per high-dose and

placebo arm (exact number will be known at the unblinding at the end of the trial). This is due to the fact that patients that are already randomized to the study (approximately 38) will have a treatment period of 4 weeks while future randomized patients (approximately 100) will have a treatment period of 12 weeks.

Section 1.4 (Study Design) has been updated to reflect this change, however, the updated numbers are reflected in all relevant sections of the CSP.

Interim analysis

The interim analysis is updated as follows: The text is revised to alter the futility interim analysis to two administrative interim analyses for internal decision making. The futility analysis has been removed to be able to evaluate the sustained effect on u-LTE₄ at 12 weeks. The focus of the study extended to 12 weeks aiming on evaluation 5-LO pathway inhibition, ie not only at the end of 4 weeks but at the end of 12 weeks to ensure the use of the drug in a chronic setting. The futility analysis has therefore been changed into two administrative interim analyses for internal decision making. In the event of positive outcome at any of the administrative interim analyses an evaluation of exposure-response relationship may be performed. This is reflected in the Study Synopsis (Statistical methods) and Section 8.5.6 (Interim analysis).

Biomarker sampling

An additional biomarker sample will be collected at day 2 after the ACS.

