1.4 Study Design

This is a randomized, single-blind, placebo-controlled, parallel-group, multicentre study in subjects with CAD.

NB. The study was originally designed to be a 4-week study and was amended to be a 12-week study. As a consequence, some patients will have a treatment period of 4 weeks only while others will have a treatment period of 12 weeks. Visits 4b and 4c only apply to patients included under the amended CSP.

The study will be conducted at approximately 10 centres in 3 countries (Denmark, Finland and Sweden).

Patients suitable for the study will be identified and screened for eligibility after being hospitalized for ACS (Visit 1) comprising STEMI or NSTEMI. At Visit 1, after signing informed consent, biomarker sampling will take place at days 1, 2, 3 and 5 post ACS, where feasible. It is planned that approximately 138 CAD patients will be randomized to ensure at least 66 evaluable patients receiving AZD5718 [REDACTED] or placebo are included with 12 weeks treatment. An evaluable patient is defined as a patient with a valid CFVR measurement at Visit 2 (baseline) and one postbaseline visit as judged by the CFVR Core lab. For supporting dose selection in future studies, a treatment arm with 20% of randomized patients receiving AZD5718 [REDACTED] is included in the study.

On Day 1 (Visit 2), 7-28 days after the ACS event, patients willing to participate in the study will complete the screening procedure and, if eligible, be randomized in a ratio 2:1:2 to receive either AZD5718 (██████), AZD5718 (██████) or Placebo. Treatment duration will be 12 weeks, once daily administration in the morning. Dose on Visit 2 (Day 1), Visit 3 (2 weeks), Visit 4 (4 weeks), and Visit 4c (12 weeks) will be given by study personnel at the study site.

[figure not shown]
During the treatment phase, patients will come in to the clinic for study measurements at 2 weeks (Visit 3), 4 weeks (Visit 4), 8 weeks (Visit 4b) and 12 weeks (Visit 4c).

A follow-up visit (Visit 5) will be performed at 4 weeks (± 4 days) after last dose in order to ensure safety and well-being of the patients.

[figure not shown]
Study overview is presented in [Figure 1](#) below. For details and timings of the study assessments refer to [Table 1](#) Section 4.

Based on emerging data from the study AstraZeneca may decide to use the plasma/serum and/or urine samples collected in the study to address other study objectives than the pre-specified for a specific sample.

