3.9 Discontinuation of investigational product

Patients may be discontinued from IP in the following situations:

- Patient decision. The patient is at any time free to discontinue treatment, without prejudice to further treatment
- An adverse event that, in the opinion of the Investigator or AstraZeneca, warrants discontinuation from further dosing
- Patient noncompliance that, in the opinion of the Investigator or sponsor, warrants withdrawal (e.g. refusal to adhere to scheduled visits)
- Patient is determined to have met one or more of the exclusion criteria or failed to meet all of the inclusion criteria for study participation at study entry and continuing IP, in the decision of the Investigator, might constitute a safety risk

If the patient is discontinued from IP, the scheduled study visits, data collection and procedures should continue according to the Clinical Study Protocol (CSP) until study closure. Alternatively, if the subject does not agree to this option, a modified follow up through e.g., regular telephone contacts or a contact at study closure should be arranged, if agreed to by the subject and in compliance with local data privacy laws/practices. The approach taken should be registered in the CRF.

If patient is required to or chooses to discontinue the IP, every reasonable effort should be made for the patient to remain in the study for follow-up and to complete all other study procedures until the scheduled end of the study.

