Study Day	-7 days	x^a	day 1	day 14	day 28	28 days after Visit 4	28 days after Visit 4b	28 days after last dose	
Time Window		1-5 days post ACS event	7-28days post ACS event	±2	±3	±2	±3	±4 days	
Informed consent (ICF)		x							
Inclusion/exclusion criteria		x	x						
Demographic data		x							Smoking history and alcohol consumption to be included
Height		x							
Body weight ^b		x	x	x	x		x	x	
Collect date for ACS event		x							
TIMI flow score		x							
Medical and surgical history		x							
Concomitant medication		x	x	x	x	x	x	x	

Table 1 Study assessment schedule

	ACS event	Visit 1 Screening	Visit 2 Randomization	Visit 3 (2 weeks) During Treatment	Visit 4 (4 weeks) During Treatment	Visit 4b (8 weeks) During Treatment	Visit 4c (12 weeks) End of Treatment	Visit 5 Follow-up	Comments
Study Day	-7 days	x ^a	day 1	day 14	day 28	28 days after Visit 4	28 days after Visit 4b	28 days after last dose	
Time Window		1-5 days post ACS event	7-28days post ACS event	±2	±3	±2	±3	±4 days	
Serology (see Table 3)		x							
FSH and luteinizing hormone (LH) sampling (females only)		x							
Randomization			x						
Diary card hand-out			x						
Diary card review				x	x	x	x		
Diary card hand-in							x		
IP dispensed			x		x	x			
IP returned					x	x	x		
IP intake at the clinic			x	x	x		x		
Safety and tolerability:									
Adverse event (AE) review		x (SAE only)	x	x	x	x ^m	x	x	

Table 1 Study assessment schedule

	ACS event	Visit 1 Screening	Visit 2 Randomization	Visit 3 (2 weeks) During Treatment	Visit 4 (4 weeks) During Treatment	Visit 4b (8 weeks) During Treatment	Visit 4c (12 weeks) End of Treatment	Visit 5 Follow-up	Comments
Study Day	-7 days	x ^a	day 1	day 14	day 28	28 days after Visit 4	28 days after Visit 4b	28 days after last dose	
Time Window		1-5 days post ACS event	7-28days post ACS event	±2	±3	±2	±3	±4 days	
Blood pressure and pulse rate (supine)		x	x	x	x		x	x	
12-lead pECG with electronic source file		x	x	x	x		x	x	
Physical examination ^c		x	x	x	x		x	x	
Blood and urine samples for safety laboratory evaluations (including fasting glucose) ^d		x ^{e,n}	x ^f	x ⁿ	x		x	x	
Efficacy Assessments:									
Spot urine for analysis of LTE ₄ levels and urinary creatinine		x ^l	x ^g	x (pre-dose)	x (pre-dose)		x(pre-dose)	x	Screening sample will not be used for assessment of primary endpoint

Table 1 Study assessment schedule

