6.2.2 Windows

For the purpose of statistical analysis and if not otherwise specified, all the efficacy variables (primary, secondary and exploratory variables) and all the safety variables (Clinical laboratory evaluations, ECGs, Vital Signs and Physical examinations) will be assigned to the visit in which they are collected depending on the following analysis visit windows.

Analysis visit (AVISIT)	Scheduled visit day	Visit Window for Analysis (Days)
Baseline ^b	1	<]ª
Baseline Post-dose ^c	1	1
Visit 3	14	$10 - 18$ and $\leq = $ last dose
Visit 4	28	23 - 33 and <= last dose + 3
Visit 4b	56	49 – 63 and <= last dose
Visit 4c	84	74 – 94 and <= last dose + 3
Visit 5 – FUP 1 month	56 / 112	>=last dose + 24

Table 3: Visit windows

^a Includes also measurements collected at day 1 prior to first dose of IP for all variables except PRO questionnaires, ECGs, Vital Signs and Physical examinations. For PRO questionnaires, ECGs, Vital Signs and Physical examinations, all the measurements collected at day 1 will be considered as baseline measurements as per protocol. For uLTE₄ and cardiovascular biomarkers, the baseline will be the last available value before the first dose of treatment, among the values collected after the ACS event +7 days (included).

^b Analysis visit will be labelled "Baseline Pre-dose" for PK measurements.

^c Only applicable to PK measurements occurring on Day 1 after the first dose.

Measurements collected outside the visit windows will be labelled as "Unscheduled visit". For uLTE₄, urine creatinine, Creatinine-normalized u-LTE₄ and Cardiovascular biomarkers, measurements collected from date of ACS event to 6 days post ACS will be labelled as "Screening".

Distribution:

Original:

Copy:

TPCA025 Version 2 (based on TPQA036 Version 2)

STATISTICAL ANALYSIS PLAN

Sponsor:	AstraZeneca AB	Protocol/CIP Number:	D7550C00003
CIL Project Number:	40343		

In general, the baseline value used for statistical analyses is the last available value among those in the Baseline visit windows, prior to first dose of IP, except for PRO questionnaires. Additional details for baseline assessment will be given in section 6.3.

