For visit windows 3, 4, 4b, 4c and 5 if more than one measurement of the variable (scheduled or unscheduled visit) falls in the same visit window but in different days, the nearest to the scheduled visit day will be taken. If several measurements are collected within the same distance from the scheduled study day, the data of the latest visit after the scheduled study day within that window will be used.

If several measurements are collected during the selected day, the average (for numeric values)/worst (for categorical values) of the measurements will be taken. For numeric values, the analysed value will be the arithmetic mean for normal distributed variables and the geometric mean for log-normal distributed variables.

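### SAP Table 3 ties Visit 5 to a fixed study day with no upper limit, so some 12-week patients who stop early have a later off-drug value tabulated as the one-month follow-up

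*SAP*

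**What the plan says.** Protocol section 1.4 defines the visit by last dose: "A follow-up visit (Visit 5) will be performed at 4 weeks (± 4 days) after last dose". The schedule in protocol section 4.1 (Table 1) repeats this as "28 days after last dose".

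Protocol section 3.9 keeps patients who stop study drug in follow-up: "the scheduled study visits, data collection and procedures should continue according to the Clinical Study Protocol (CSP) until study closure".

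SAP section 6.2.2 (Table 3) treats Visit 5 differently. Its scheduled day is 56 or 112, counted from first dose. Its window starts at last dose + 24 days and has no upper limit. The paragraph after the table names Visit 5 among the windows in which, if more than one measurement "falls in the same visit window but in different days, the nearest to the scheduled visit day will be taken". If two are equally near, "the data of the latest visit after the scheduled study day within that window will be used".

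The Visit 4c window is "74 – 94 and <= last dose + 3". An early stopper's day-84 data therefore cannot be labelled Visit 4c if they were taken more than 3 days after last dose.

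SAP section 5.2, which lists departures from the protocol, does not mention the Visit 5 anchor or its open window.

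**The concern.** The Visit 5 window follows last dose but its anchor follows first dose. They agree only for patients who finish treatment on schedule. For someone who stops early and keeps attending, the nearest-day rule pulls towards day 112, and so towards the later of two off-drug values.

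Visit 5 is the planned safety follow-up. The laboratory shift and Hy's law tables use on-treatment values, which end 7 days after last dose (SAP sections 6.2.3, 6.6.3 and 8.8.3). Protocol section 6.3.6 makes deterioration in a mandated laboratory test or vital sign an adverse event only if it meets a seriousness criterion or leads to stopping study drug; otherwise any associated sign or symptom is what gets reported. An asymptomatic, non-serious abnormality four weeks off drug would therefore be tabulated mainly in the by-visit Visit 5 summary, which is where this rule can substitute a later value.

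**Working it through.** **Inputs.** L is the study day of last dose.

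- Anchor A: day 56 (4-week cohort) or day 112 (12-week cohort); window: day ≥ L + 24 (SAP Table 3).
- Protocol timing of Visit 5: L + 28, allowed range L + 24 to L + 32 (protocol sections 1.4 and 4.1).
- Scheduled visits with samples: days 14, 28 and 84. The day-56 visit (Visit 4b) has no scheduled sampling.
- Visits 4b and 4c exist only in the 12-week cohort: "Visits 4b and 4c only apply to patients included under the amended CSP".

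**Reproducing the SAP figures.** 28 + 28 = 56 and 84 + 28 = 112, so each anchor equals last dose + 28 for an on-schedule completer. The lower limit is 28 − 4 = 24. The matching upper limit, 28 + 4 = 32, is absent.

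**Applying the rule, 12-week cohort.** Suppose the patient is seen at L + 28 and at day 84. Day 84 lies in the Visit 5 window if 84 ≥ L + 24, that is L ≤ 60. It lies 112 − 84 = 28 days from the anchor. The follow-up value lies 112 − (L + 28) = 84 − L days from it. Day 84 is chosen when 28 < 84 − L, that is L < 56. The chosen value is then 84 − L days off drug and 56 − L days later than the 28-day value.

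| Last dose L | Follow-up day L + 28 | Its distance to 112 | Distance of day 84 | Chosen day | Days off drug | Later by |
|---|---|---|---|---|---|---|
| 14 | 42 | 70 | 28 | 84 | 70 | 42 |
| 28 | 56 | 56 | 28 | 84 | 56 | 28 |
| 42 | 70 | 42 | 28 | 84 | 42 | 14 |
| 50 | 78 | 34 | 28 | 84 | 34 | 6 |
| 55 | 83 | 29 | 28 | 84 | 29 | 1 |
| 60 | 88 | 24 | 28 | 88 | 28 | 0 |

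The 28-day value is displaced for every L from 1 to 55. The chosen value falls outside 24 to 32 days off drug when 84 − L > 32, that is for L up to 51. Over that range it is 33 days (L = 51) to 83 days (L = 1) off drug. The delay is at least 14 days for L up to 42.

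**A single value in the window.** If day 84 is the only later attendance, nothing is displaced, but the value still takes the one-month label. For L = 30 it is 84 − 30 = 54 days off drug.

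**4-week cohort.** No scheduled visit follows L + 28, so scheduled visits displace nothing. The protocol's version history says that "patients that are already randomized to the study (approximately 38) will have a treatment period of 4 weeks".

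**After the change.** With the anchor at L + 28 and the window at L + 24 to L + 32, the 28-day value is chosen for L = 14, 28, 42 and 55. At L = 55 the candidates are days 83 and 84, and day 83 is nearer. Completers keep day 56 or 112.

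**The case against.** The strongest reply is that displacement needs two attendances after stopping, and the protocol does not clearly create them. Section 3.9 asks patients to follow the schedule to its end, and Table 1 has one Visit 5, placed after Visit 4c. An early stopper who follows that sequence has a single Visit 5 near day 112, which is the SAP's anchor. This stands in part. The protocol does not say whether such a patient has Visit 5 four weeks after last dose or at the end of the schedule, although the literal definition points to last dose. On the end-of-schedule reading nothing is displaced, but the label is still wrong: for L = 28 the value is 112 − 28 = 84 days off drug.

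The reply also limits what may be claimed. A reader might infer any of the following, and the documents do not support them:

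- That the 28-day value is lost whenever a patient stops early. On scheduled visits there is no displacement in the 4-week cohort, for last doses on days 56 to 83, or with one value in the window. Displacement by a day-112 sample needs an assumed extra visit.
- That about 0.18 × 40 = 7 patients per arm are affected. The 18% in protocol section 8.2 is an allowance for non-evaluable patients, where evaluable means a valid CFVR at baseline and at one later visit. It is not a rate of stopping drug while still attending.
- That off-drug abnormalities would be hidden. Laboratory and vital-sign data are listed (SAP sections 8.8.3 and 8.8.4), as are the efficacy variables, and adverse events are assigned by time from last dose, with separate off-treatment tables. What can be missing is the 28-day value in the summary tables.
- That efficacy conclusions are at risk. The u-LTE₄ models use Visits 2, 3, 4 and 4c and the CFVR models Visits 2, 4 and 4c; none uses Visit 5.

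**Conclusion.** The point holds in a limited form. For 12-week patients with last dose on days 1 to 55 who are seen at last dose + 28 and again at day 84, the SAP replaces the 28-day value with a later one. For last doses up to day 51 the tabulated one-month value is 33 to 83 days off drug, and the error always runs towards later values. A lone day-84 value is mislabelled in the same way over that range.

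The effect is confined to descriptive by-visit Visit 5 summaries: laboratory tests, vital signs, u-LTE₄, biomarkers, echocardiography and cfPWV/bPWA. The conclusion assumes nominal visit days and, for displacement, that the early stopper attends both visits. The documents do not give the number of such patients. This is a small, avoidable mismatch between SAP and protocol in the follow-up tables.

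**What to change.** In SAP Table 3, set the Visit 5 scheduled day to last dose + 28 and apply the nearest-day rule to that anchor. Bound the window, for example at last dose + 24 to + 32, which is the protocol's own tolerance, or at a somewhat wider stated limit. Give later off-drug values their own analysis label, such as late off-treatment follow-up, so that they are still summarised. Record the change in SAP section 5.2.

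Separately, protocol sections 1.4, 3.9 and 4.1 need to be reconciled on when a patient who stops study drug early but stays in the study has Visit 5.

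The cost is one table row, one extra label and minor programming. The downside is that an early stopper seen only late would have no value in the one-month row; that value would appear under the new label and in the listings.

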6.2.3 Phase

For the purpose of safety analyses, analysis phase will be defined in terms of study days since the first day of the study medication, as illustrated in the following table:

Phase	Phase Window for Analysis (Days)
Baseline phase	before first dose of study IP (day <1 ^a)
On-treatment phase	From day 1^{b} to ≤ 7 days after last dose of study drug
Off-treatment phase	>7 days after last dose of study drug

Table 4: Analysis phases

a Includes all measurements collected before first dose of IP. If the measurement is collected on the day of first dose of IP but the time of collection (or the planned timepoint) cannot determine if the measurement was before or after first dose of IP, then it will be considered as collected after first dose of IP except for ECGs, Vital Signs and Physical examinations which are considered as pre-dose measurements as per protocol.

^b Includes all measurements collected on the day of first dose of IP (Day 1), at the time of IP intake and after.

6.3 **Baseline Assessments**

The baseline value used for statistical analyses is the last available value among those in the Baseline visit windows, prior to first dose of IP, except for PRO questionnaires. As reported in the footnote (a) of table 4, if the measurement is collected on day 1 but it cannot be determined if the measurement was done before or after the first dose of IP (due to missing time or planned time point flag or missing time of first dose of IP), then it will be considered as collected after the first dose of IP. There is one exception to that for ECGs, Vital Signs and Physical examinations which are considered as pre-dose measurements as per protocol. If several measurements are collected on the last date (same day) prior to the first day of IP, or on the first day of IP prior to the first dose, the baseline value will be the average (for numeric values)/worst (for categorical values) of the measurements.

	Distribution:	Original:	Copy:
TPCA025 Vers (based on TPQA	2 3		Effective Date: 27 th August 2017 Prior Effective Date: 21 st December 2016

CONFIDENTIAL AND PROPRIETARY

Sponsor:	AstraZeneca AB	Protocol/CIP Number:	D7550C00003
CIL Project Number:	40343		

For uLTE₄ and cardiovascular biomarkers, screening measurements (from ACS event to 6 days post ACS event included) cannot be used as baseline values. For these variables the baseline will be the last available value before the first dose of treatment, among the values collected after the ACS event +7 days (included). If the measurement is collected on day 1 but it cannot be determined if the measurement was done before or after the first dose of IP (due to missing time or planned time point flag or missing time of first dose of IP), then it will be considered as collected after the first dose of IP. If several measurements are collected on the last date (same day) prior to the first day of IP, or on the first day of IP prior to the first dose, the baseline value will be the average of the measurements.

For PRO questionnaires, the baseline is the value collected before or on day 1. If several measurements are collected on the same day, the baseline value will be the average of the measurements.

The following will be evaluated as baseline assessments at visit 1 (screening visit):

- Demographics (age (years), age group (<50; >=50 -<65; >=65 years), race, ethnicity, sex, weight (kg), weight group (<70; >=70- <90; >=90 kg), height (cm), BMI (kg/m2), BMI group (Normal <25; Overweight >=25-<=30; Obese >30 kg/m2) and country.
- Relevant medical and surgical history
- Specific medical and surgical history
- Nicotine use and alcohol use, consumption and frequency
- Allowed concomitant medications

6.4 Efficacy Variables

6.4.1 Primary Efficacy Variable(s)

Spot urine for analysis of LTE₄ levels (pmol/L) and urinary creatinine (mmol/L) will be collected at Visit 1, Visit 2, Visit 3 (pre-dose), Visit 4 (pre-dose), Visit 4c (pre-dose) and Visit 5. Primary efficacy variable is the Creatinine-normalized u-LTE₄ (pmol/mmol) which will be calculated as the u-LTE₄ / urinary creatinine. If the u-LTE₄ value falls under the limit of quantification (LoQ) then creatinine-normalized u-LTE₄ will be calculated as the limit/(sqrt(2)*creatinine). LoQ value will stated in the raw data.

The primary efficacy endpoint is the change at visit 4 (4 weeks) from Baseline in creatininenormalized u-LTE₄. The first secondary efficacy endpoint is the change at visit 4c (12 weeks) from Baseline in creatinine-normalized u-LTE₄.

Baseline Creatinine-normalized u-LTE4 value is defined as in section 6.3.

Creatinine-normalized u-LTE₄ is potential unblinding data. For the interim analysis these data will be provided only to the dedicated Covance unblinded team which will perform the analysis and send the results to the dedicated AZ unblinded team. Further details of the unblinding will be provided in the IA charter. For the final analysis these data will be provided to the Covance blinded team only after the database lock.

Distribution:

Original:

Copy:

TPCA025 Version 2 (based on TPQA036 Version 2)

Sponsor:	AstraZeneca AB	Protocol/CIP Number:	D7550C00003
CIL Project Number:	40343		

